5.2 Recruitment Methods

Aim 1 Recruitment and retention procedure for Clinical Psychologists: We aim to recruit 6 VA clinical psychologists who self-report experience in CBT, anxiety, and in treating Veterans. We will recruit through emails to colleagues who work with VA clinical psychologists.

Recruitment and retention procedure for Veterans (Aims 1 & 2): We aim to recruit 6 eligible Veterans for Aim 1 and 15 eligible Veterans for Aim 2 from the Canandaigua VA. A two-pronged recruitment strategy will be employed: 1) VA healthcare providers will be able to refer potentially eligible participants by placing the investigators as additional signers on notes using the VA's electronic medical record. To facilitate recruitment, we will present on the intervention at staffing meetings held at various clinics. 2) Veterans with anxiety disorder diagnoses, identified using ICD codes, who are enrolled at the study site will be identified using structured queries of VA administrative datasets. Potential participants will be mailed a personalized letter describing the study and providing a toll-free number so that they can contact study staff if they are interested in participating as well as opt out of future contact. A study flyer will be included with this letter. There will be a QR code on this flyer directing participants toward our screener on Qualtrics that potential participants can complete instead of contacting study staff. We will use several procedures known to promote retention in longitudinal studies.¹⁻⁴

Web-based study screening:

One mode for determining study eligibility will be Qualtrics (www.qualtrics.com), a web-based survey platform. Qualtrics is a popular tool for collecting survey data online with the ability to implement sophisticated study designs. People interested in completing the screening form via Qualtrics will scan the QR code on the flyer which will direct participants to several brief screening questions to ascertain study eligibility, made up of IRB-approved study measures. If eligible and interested, participants can request to be contacted by study staff. All respondents are encouraged to call the toll-free number with any questions/comments /concerns prior to enrolling in the study.

Screening Data. Participants will be asked several questions to confirm eligibility and asked to answer several multiple-choice questions in Qualtrics (or by phone). The information will be stored separately from study data in a password-protected database. Data will be encrypted and stored behind the VA firewall. To enhance data security, access to study data will be limited to IRB approved study personnel. None of these data will be linked to research data.

Self-Report Survey. Data collected for this project will be obtained by online survey. No identifiable data will be included in the limited data set, and a unique identifier will be assigned to each of the records to be used for analysis. Data will then be encrypted stored behind the VA firewall for cleaning and analysis in VINCI. To enhance data security, access to study data will be limited to IRB approved study personnel.

Any recruitment, screening, or payment-related documents will be stored separately (in ‘access restricted’ file) from study data when received by VA behind VA firewall.

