Payments will be made via direct deposit, check, or debit card following each study procedure listed above. Participants who do not complete the entire study for any reason will receive compensation for the components that were completed per the above schedule of payments.

VA Clinicians recruited for Aim 1 will not be compensated, instead providing their effort in kind.

Aim 2 Design

Study Sample and Screening: We will recruit 15 Veterans with elevated anxiety sensitivity (i.e., SSASI ≥ 9) and moderate or higher functional impairment (12-item World Health Organization Disability Assessment Schedule 2.0 $\geq 5^9$). Additional criteria include English-speaking and 18 years of age or older. Veterans do not need to meet diagnostic criteria for an anxiety disorder to benefit from BEAST and therefore the presence of an anxiety disorder is not an inclusionary criterion. Further, because BEAST targets a construct that is non-overlapping with constructs targeted in traditional CBT, Veterans are eligible regardless of current treatment status. The Project Coordinator will conduct all screening and assessments by phone or video call following a script. Potential participants will provide verbal consent to complete the screening measures. Veterans meeting eligibility and interested in participating will be scheduled for a consent and baseline assessment appointment.

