5.5 Study Evaluations

Consistent with recommendations for determining acceptability and feasibility in the context of intervention development, multiple program aspects will be evaluated with the aim of refining BEAST for larger-scale implementation.^{15–17} Feasibility of BEAST will be indexed via participant retention, average homework completion, and percentage of EMA sessions completed.

Acceptability will be measured using an adaptation of the Program Satisfaction Questionnaire (PSQ), a 14-item measure that assesses both general program satisfaction (usefulness, acceptability) and perceived utility of program components (psychoeducation, EMA/EMI schedule).¹⁸ Measures selected were well-validated, have been administered to Veterans, and/or have been administered via telehealth.

Assessments completed via research staff:

Program Satisfaction Questionnaire (PSQ). Acceptability will be measured using an adaptation of the PSQ, a 14-item measure that assesses both general program satisfaction (usefulness, acceptability) and perceived utility of program components (psychoeducation, EMA/EMI schedule).¹⁸

Blessed Orientation-Memory-Concentration Test (BOMC). The BOMC will be used to screen for cognitive impairment (i.e., ≥ 11).¹⁹

Short Scale Anxiety Sensitivity Index (SSASI).²⁰ The SSASI is a 5-item self-report measure assessing fear of negative consequences of anxiety-related symptoms. Scores ≥ 9 on the SSASI are eligible.

The Anxiety Sensitivity Index-3 (ASI-3).²¹ The ASI-3 is an 18-item self-report measure assessing fear of negative consequences of anxiety-related symptoms.

The Intolerance of Uncertainty Scale-12 (IUS-12).²² The IUS-12 is a 12-item self-report measure assessing fear of uncertainty.

12-Item World Health Organization Disability Assessment Schedule (WHODAS) 2.0. The 12-item version of the WHODAS 2.0 assesses functional impairment across six domains: 1) understanding and communication, 2) self-care, 3) mobility, 4) interpersonal relationships, 5) work and household roles, and 6) community and civic roles.²³

PROMIS Profile-29²⁴. Used to assess the following domains: anxiety, depression, physical function, fatigue, sleep disturbance, ability to participate in social roles and activities, and pain interference.

Functional Impairment Due to COVID (FIDC).²⁵ A 7-item measure adapted from the WHODAS 2.0 to capture difficulties in functioning due to the COVID-19 pandemic, developed and validated by PI [name] and colleagues.

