COVID-19 Impact Battery (CIB) Worries.²⁵ An 11-item scale measuring distress and worry due to the COVID-19 pandemic.

COVID-19 Impact Battery (CIB) Behaviors.²⁵ A 12-item scale assessing avoidance behaviors in relation to the COVID-19 pandemic.

Depressive Symptom Index – Suicidality Subscale (DSI-SS). A 4-item measure assessing suicidality within the previous two weeks.

Demographics. At screening, we will assess participants' gender, age, educational background, employment, income, race, ethnicity, marital status, and socioeconomic status.

Exit Interview. The exit interview will assess overall impressions, impact of treatment, relationship with the therapist, and ways to improve the treatment. Acceptability will be measured using an 11-item adaptation of the Program Satisfaction Questionnaire (PSQ) that assesses both general program satisfaction (usefulness, acceptability) and perceived utility of program components (psychoeducation, EMA/EMI schedule).¹⁸ The exit interview and PSQ will inform further refinement of the intervention as needed with our stakeholders. The exit interview will also consist of a number of open ended questions, including prompts to ask for more information, to collect worthwhile feedback on the study procedures, intervention, and their overall feelings toward the intervention.

EMA Measures:

*State Short Scale Anxiety Sensitivity Inventory; SSAS*²⁰: measures anxiety sensitivity.

*State Penn State Worry Questionnaire; PSWQ*⁵¹: measures anxious apprehension.

State Anxiety Depression Distress Inventory-27; ADDI-27: measures anxious arousal

The PSWQ and ADDI-27 have been validated as measures of general anxious apprehension and anxious arousal, respectively, reflecting the two core anxiety dimensions underlying anxiety disorders.^{26,27} Participants will also rate their impairment across functional domains using the

12-item WHODAS 2.0. Visual analog scale (VAS) ratings from 1-100 will be used to assess anxiety, stress, and depression four times daily. ASI-3 items, revised to capture in-the-moment beliefs, will also be completed. Three items will be randomly selected from an ideographically developed pool of items the participant rates as impacting them “much” or “very much.” Thus, the pool of items to be drawn to potentially deliver EMI will differ by individual.

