5.7 Data Analysis

General. To enhance methodological rigor and to allow for accurate dissemination of our findings, we will follow CONSORT guidelines in the design, analysis, and reporting of this study.

Data Management. [name], with the assistance of Drs. [name] and [name], will supervise data management using the following services: Enrollment, randomization, tracking of interviews, and auditing of data. A single enrollment and randomization document will be developed to assign identification codes to participants during the pre-enrollment period to track their eligibility status, and randomly assign participants. Similar to our prior studies, a tracking system will be developed to assist research personnel in managing follow-up interviews. This information will be covered during weekly staffing meetings involving Drs. [name], [name], and [name] as well as the research personnel. Data will be audited for: a) data quality control (% of scales returned for corrections after auditing); b) rate of data entry; and c) backlog of data that has not been entered. All scales will be audited for identifiers, item completeness, and consistency of major clinical indicators. We will store and manage data at the VA with access limited to pertinent study personnel. During the study, we will maintain a dialogue on the technical integrity of our procedures and on conceptual aspects of our project.

Data analysis for Aim 1: Develop expert consensus for our intervention components using a modified Delphi method. Specifically, a modified Delphi Method will facilitate the incorporation of expert and stakeholder feedback to reach consensus.^{38,39} We will present to our stakeholders the results of our study and any proposed changes as-needed after we complete Aim 2 (one-arm trial). Experts and stakeholders will rate each component as: a) acceptable as is, b)

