The PI will check the work of the raters and chart the data to further examine the domains, core ideas, and categories that describe the themes. Means and standard deviations for outcomes will be calculated at each assessment, including change scores and correlations across timepoints. We expect large standard errors due to sample size. Distribution of scores will be examined to better evaluate how to analyze these data in future studies. For continuous outcomes, Hedge's g will be calculated to identify a range of the pre-post effect size. Although such calculations are of limited benefit in determining the effect of the intervention, they are helpful in identifying outcomes for which the intervention may be less effective.

For data quality and handling of missing data, descriptive statistics will help identify out of range values and outliers. *The assessment battery* will be considered acceptable if no questionnaires are missing in full in more than 25% of the participants and if reliability is higher than 0.70. *Acceptability of EMA procedures* will be assessed through calculating the percentage of EMA surveys completed as well as completion patterns. BEAST will also be considered feasible and acceptable if $\geq 70\%$ of the EMA sessions are completed by $\geq 80\%$ of participants, consistent with prior rates in studies conducted and reviewed by [name]. Acceptability will also be measured using an adaptation of the PSQ, an 11-item measure that assesses both general program satisfaction (usefulness, acceptability) and perceived utility of program components (face-to-face sessions, EMA/EMI).¹⁸ Finally, an average PSQ general satisfaction score of ≥ 4 (on a 5-point scale) and an average PSQ mobile app score ≥ 4 (on a 5-point scale) will provide support for the feasibility and acceptability of BEAST. The research team and stakeholders will

meet and discuss the intervention regarding benchmarks of acceptability and feasibility as well as the information gathered during the exit interviews.

Power analysis. As this is a pilot trial, we did not conduct a formal power analysis when selecting the sample size. Rather, we used stepped rules of thumb to optimize the overall sample size for the pilot and main effects study.²⁸ Based on these stepped rules of thumb and an expectation of clinical effect sizes in the medium range on primary and secondary outcomes of the RCT, 15 participants is considered adequate.

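### Does the rule against linking screening data leave the analysis dataset without the participant characteristics the pilot needs?

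*Combined protocol and SAP*

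**What the plan says.** Section 5.2, under Screening Data, covers the eligibility questions asked through Qualtrics or by phone. It puts the answers in their own password-protected database and adds: "None of these data will be linked to research data". The same section later repeats the separation: "Any recruitment, screening, or payment-related documents will be stored separately". Neither sentence distinguishes people who enrol from people who do not.

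Section 5.5 lists the demographic items with the words "Demographics. At screening, we will assess" and names no other time for collecting them. For the cognitive test it says only that "The BOMC will be used to screen for cognitive impairment". Section 5.1 (Aim 2) gives screening its own consent step: "Potential participants will provide verbal consent to complete the screening measures".

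Section 5.7 points the other way. It states that "we will follow CONSORT guidelines in the design, analysis, and reporting of this study", and it plans a single enrolment document that will "assign identification codes to participants during the pre-enrollment period to track their eligibility status". On EMA, it says acceptability "will be assessed through calculating the percentage of EMA surveys completed as well as completion patterns".

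**The concern.** Taken together, the sentences seem to shut the description of the sample out of the analysis file. Demographics are gathered at screening, screening data may not be linked, and so the coded dataset would hold no age, sex, race or education for anyone. A study that commits to CONSORT will be expected to say who took part. Section 6.0 also says the recruitment lists will be used to increase the numbers of high-risk Veterans, women and minorities, and a reader will want to know whether that happened.

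The pilot is meant to inform a later RCT. If some Veterans drop out or complete few EMA surveys, it would help the designers to know whether they were, say, older or nearer the BOMC cutoff. That needs a link at the level of the person, which a literal reading forbids.

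**Working it through.** The question is one of data flow, and the plan has no figure to reproduce. The check is to see what the rule removes, what remains, and whether any planned result depends on what is removed.

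**1. What a literal reading removes.**
- Demographics (Section 5.5): gender, age, education, employment, income, race, ethnicity, marital status, socioeconomic status. That is 9 variables, and 9 of 9 are placed at screening.
- The BOMC score, whose only stated use is as a screen.
- The screening-occasion scores on the SSASI and the 12-item WHODAS 2.0.

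**2. What remains.**
- Section 5.1 has a baseline assessment after consent, separate from screening.
- Section 5.7 computes outcome summaries and change scores across assessments and a pre-post Hedges' g, so baseline outcome scores must be in the coded data.
- Section 5.5 includes a state version of the SSASI and the 12-item WHODAS 2.0 among the EMA measures. Section 5.1 starts EMA at baseline, with about one week of surveys. Anxiety sensitivity and functional impairment are therefore measured again before the session.

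The dataset thus keeps its clinical characteristics. What it lacks, on this reading, is demographics and the BOMC score.

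**3. Whether a planned Aim 2 result needs what is removed.**

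| Planned result (Section 5.7) | Source | Needs demographics or BOMC? |
|---|---|---|
| Recruitment per month | Tracking records | No |
| Completion of protocol and follow-ups | Tracking records | No |
| Therapist fidelity and inter-rater reliability | Session recordings | No |
| Battery: missing questionnaires, reliability | Assessments | No |
| EMA: at least 70% of sessions by at least 80% of participants | App data | No |
| PSQ averages of at least 4 | Post-intervention assessment | No |
| Outcome summaries, change scores, Hedges' g | Baseline and later assessments | No |

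The EMA rule requires 0.80 × 15 = 12 participants, so up to 15 − 12 = 3 may fall short while the benchmark is met. That count comes from the app alone. The completion patterns named in Section 5.7 are patterns of survey response, and the text ties them to no demographic variable.

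**4. Whether the sample can still be described.** The screening records are kept, and the enrolment document carries identification codes and eligibility status from before enrolment. Once the screening records show who enrolled, a summary of the 15 follows without moving any item into the research file. Such a summary would also answer the sex and race/ethnicity part of the recruitment aim in Section 6.0, which sets no numerical target. Eligibility can be audited from the same records.

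**The case for a change.** The strongest case for a change is that the text pulls in two directions. One section forbids linking and another plans a code that makes it possible, so staff cannot tell which governs. Screening has its own consent, and linking later on an assumed exception could depart from approved wording. An aggregate table cannot show whether the Veterans who missed the EMA threshold share a characteristic. The remedy would be cheap, and the loss might be hard to make good afterwards.

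Part of this stands. The rule has no written exception, screening is the only stated time for demographics, and person-level description is lost if the rule is applied to the letter.

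The rest is weaker. The literal reading is not the only one. The no-link sentence follows directly on the description of the web-based eligibility screener, while the demographics are listed in Section 5.5 among the assessments done by research staff. Income, education and marital status are not eligibility criteria. The mention of phone screening blurs that distinction without removing it. Consent pages were taken out of the reviewed text, so silence about how enrollees' screening data may be used cannot be counted as an omission. Listing the traits of at most 3 Veterans who miss the EMA threshold, at one site, would support no inference and carries a small-cell confidentiality cost.

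**Conclusion.** No change to the plan is called for. The wording about linking is looser than it should be, and the literal consequence is limited: 9 demographic variables and the BOMC score would sit outside the coded dataset for 15 people, while baseline clinical and EMA measures would sit inside it. No benchmark, effect size or feasibility conclusion moves, because none uses the excluded items. The sample can be described in aggregate from records the plan already keeps.

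This rests on two assumptions. The first is that enrolment status can be identified within the screening records, which the pre-enrolment codes make practicable. The second is that the team adds no subgroup or covariate analysis by demographics; none is planned. If the rule was meant only for people who screen and do not enrol, as the codes suggest, then even the person-level description is not lost.

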5.3 Informed Consent Procedures

There are three phases where informed consent could be obtained, when stakeholders are reviewing the intervention (Aim 1), when completing the screening for eligibility and when enrolling into the study following the screening and if eligibility criteria are met (Aim 2). Verbal consent to participate will be obtained for all participants. Informed consent will be obtained by study personnel trained in human subjects’ protections requirements and how to obtain and document informed consent. Further, questions are embedded at the end of the consent form requiring potential participants to demonstrate comprehension of what they are being asked to do.

5.4 Inclusion/Exclusion Criteria

Aim 1 Eligibility Criteria

Eligibility Criteria for 6 Veterans:

Inclusion criteria: Participants will include men and women Veterans who:

- Are English-speaking
- Are 18 years of age or older
- Score ≥ 9 on the SSASI indicating elevated anxiety sensitivity
- Score ≥ 5 on the 12-Item WHODAS 2.0

Exclusion criteria: Veterans will be excluded on the basis of:

- Veterans with cognitive impairment as measured scoring ≥ 11 on the Blessed Orientation-Memory-Concentration Test
- Veterans without access to a smartphone
- Veterans with significant medical or psychiatric conditions that may limit participation, including severe documented schizophrenia, an ongoing active psychotic or manic state, or an imminent suicide crisis will be excluded from our study and provided the appropriate referral.

Eligibility Criteria for 6 therapists

Inclusion criteria: Participants will include masters-level or higher therapists who:

- Are English-speaking
- Are 18 years of age or older
- Report experience in telehealth
- Report experience in CBT treatment of Veterans with anxiety

Aim 2 Eligibility Criteria:

Inclusion criteria: Participants will include men and women Veterans who:

- Are English-speaking
- Are 18 years of age or older

- Score ≥ 9 on the SSASI indicating elevated anxiety sensitivity
- Score ≥ 5 on the 12-Item WHODAS 2.0⁹

Exclusion criteria: Veterans will be excluded on the basis of:

- Veterans with cognitive impairment as measured scoring ≥ 11 on the Blessed Orientation-Memory-Concentration Test^{14,43}
- Veterans without access to a smartphone
- Veterans with significant medical or psychiatric conditions that may limit participation, including severe documented schizophrenia, an ongoing active psychotic or manic state, or an imminent suicide crisis will be excluded from our study and provided the appropriate referral.

Pregnant women will not be excluded from this study as no invasive medical procedures are being performed and there is no known risk to the mother or the fetus of the proposed interventions. The study will not include prisoners or institutionalized veterans.

